6.1.3.5 Categorical analysis of Hb values

The following endpoints will be analyzed:

- Proportion of Hb values \geq 10 g/dL and within 10.0-12.0 g/dL by time intervals;

- Percentage of time with Hb values falling in each Hb interval (<10.0 g/dL, >=10 g/dL, within 10.0-12.0 g/dL, > 12.0 g/dL, > 13.0 g/dL and > 14.0 g/dL) during the Efficacy Emergent Period;
- Potential Excessive Hematopoiesis (EH).

Proportion of Hb values

The following proportions in percentage for each subject will be defined:

- Number of Hb values >= 10.0 g/dL / Total number of Hb values*100
- Number of Hb values within 10.0-12.0 g/dL / Total number of Hb values*100

in weeks 28 to 36, 44 to 52 and 96 to 104 without use of rescue therapy within 6 weeks prior to and during this 8 week evaluation period. All scheduled and unscheduled hemoglobin values that belong to each period will be taken into account using the analysis windows defined in [Table 32](#) Section [7.11.4](#) The following time periods will be defined in addition: 56 to 64, 68 to 76 and 80 to 92.

Percentage of time

[figure not shown]
The percentage of time each patient has an Hb value <10.0 g/dL, >= 10.0 g/dL, within 10.0-12.0 g/dL, > 12.0 g/dL, > 13.0 g/dL or > 14.0 g/dL will be calculated (as a percentage of the total of the length of time between the first and last Hb assessment during the evaluated period). The percentage of time will be calculated via linear interpolation. That is, if the change in Hb category (for instance from <= 12.0 g/dL to > 12.0 g/dL) occurs between two visits V0 and V1, the day of change will be calculated by:

$$x = x_0 + (y - y_0) \frac{(x_1 - x_0)}{(y_1 - y_0)}$$

Where x1 and x0 are the dates when Hb was measured at V0 and V1 respectively, y0 and y1 are the Hb value at the respective visits V0 and V1 and y is the level of the Hb boundary (i.e 12.0, 13.0 or 14.0g/dL).

[Figure 1](#) shows visually how the linear interpolation will calculate the total number of days that a subject is in each Hb category for an example subject:

Figure 1 Example of Linear Extrapolation

In case that several Hb values are on the same day the average of these values will be used to represent the Hb of that day in the above formula. This calculation will provide the day that the change in Hb value occurs. The number of days that the Hb value has been in each category will be determined and the percentage calculated based on the length of time between the first and last Hb assessment during the evaluated period, i.e.:

Date of Last Hb assessment during the evaluated period – Date of first assessment during the evaluated period.

No imputation will be performed if no Hb value is available in relevant time windows.

In case a subject requires rescue therapy within 6 weeks prior to and during these 8-week evaluation periods, refer to Section 7.11.1 for imputation rules.

Potential Excessive Hematopoiesis (EH), regardless use of rescue therapy, based on Hb central laboratory

The presence of potential EH will be defined as:

- Hb increase by >2.0 g/dL between any 2 visits within 4 weeks of treatment

Time to first occurrence of potential EH regardless the use of rescue therapy during the treatment period will be defined in weeks as:

$$(\text{First event date} - \text{Analysis date of first dose} + 1) / 7$$

where ‘First event date’ is defined as first date of occurrence of the criterion met during the treatment period.

For a subject without potential EH, the time to censoring will be calculated (in weeks) as:

$(\text{Min}(\text{Date of last hemoglobin assessment during the Efficacy Emergent Period, End Date of the Efficacy Emergent Period}) - \text{Analysis date of first dose} + 1) / 7$

Refer to Section [7.11.6](#) for the definition of the Efficacy Emergent Period.

6.1.3.6 Occurrence (number) of hospitalizations, number of days of hospitalization per year and time to first hospitalization.

The occurrence and the number of non-HD hospitalizations per subject during the Efficacy Emergent Period will be calculated. HD days are not counted as hospitalizations, even when performed overnight.

The number of days of hospitalization per year treated will be calculated as:

$[\text{Sum of the durations of all non-HD hospitalizations in days (Date of discharge} - \text{Date of admission} + 1)] / (\text{duration of efficacy emergent period in days} / 365.25)$.

In case of missing dates, the hospitalization duration will be imputed by the average duration per stay derived from the subjects with non-missing duration within the same treatment group. Duration of treatment exposure is defined in Section [6.5.4](#)

If the date of admission of a hospitalization record is the same as the date of discharge of the previous record, for example because two records are created to illustrate that the subject is moved from one hospital to another hospital or from a standard care to the intensive care unit (ICU), then the two records will be combined in one record.

Hospitalizations will also be described by reason for admission (admission for anemia or other reasons).

Time to first hospitalization in years will be defined in years as:

$(\text{First event date during the Efficacy Emergent Period} - \text{Analysis date of First dose intake} + 1) / 365.25$

With 'First event date' defined as 'Date of first Admission and 'Analysis Date of first dose intake' defined in Section [6.5.4](#)

For a subject without hospitalization, the time to censoring will be calculated as:

$(\text{Date of End of Efficacy Emergent Period} - \text{Analysis Date of first dose intake} + 1) / 365.25$

With date of End of Efficacy Emergent Period defined in Section [7.11.6](#)

6.1.3.7 Occurrence and time to first use of rescue therapy, occurrence and time to first use of RBC transfusions, number of RBC packs per subject, volume of RBC transfused per subject during the treatment period.

Rescue therapy is defined as RBC transfusion for all subjects and ESA (SC or IV) for roxadustat-treated subjects.

RBC transfusion is collected and coded into the ATC and WHO-DRL dictionaries. The following WHO-DRL codes will be classified as RBC transfusion: '01186901001'. ESA rescue treatment is recorded on the dosing CRF.

Only rescue medication that started during the study treatment and up to end of efficacy emergent period will be taken into account and considered as use of rescue medication.

For a subject with use of rescue therapy, the time to first use of rescue therapy will be calculated (in years) as:

$$(\text{First event date} - \text{Analysis Date of first dose intake} + 1) / 365.25$$

With 'First event date' defined as 'Date of first dose of rescue medication' during the Efficacy Emergent Period and 'Analysis date of first dose intake' defined in Section 6.5.4

For a subject without use of rescue therapy, the Time to censoring is calculated as:

$$(\text{Date of End of Efficacy Emergent Period} - \text{Analysis date of first dose intake} + 1) / 365.25$$

With Date of End of Efficacy Emergent Period defined in Section 7.11.6

The volume of blood transfused and the total number of RBC units/packs (for each subject, the sum of blood volume and units/packs transfused) during the Efficacy Emergent Period will be calculated.

For RBC transfusions, when the number of units is not given but the volume transfused is given, the number of units will be estimated by volume transfused/250 mL (for transfusion of packed cell units) or volume transfused/500 mL (for transfusion of full blood).

For subjects with use of RBC transfusion, the time to first use of RBC transfusion is calculated as:

$$(\text{First event date} - \text{Analysis date of first dose intake} + 1) / 365.25$$

With 'First event date' defined as 'Date of first RBC transfusion' during the Efficacy Emergent Period and 'Analysis Date of first dose intake' is defined in Section 6.5.4

For a subject without use of RBC transfusion, the Time to censoring is calculated as:

$$(\text{Date of End of Efficacy Emergent Period} - \text{Analysis date of first dose intake} + 1) / 365.25$$

With Date of End of Efficacy Emergent Period defined in Section 7.11.6

The ESA-weeks are defined as the duration of ESA exposure. Each period when ESA [ATC code = B03XA] was taken will be summed by subjects as follows:

sum (each period (min(Analysis Date of last dose, End date of ESA therapy) + X days – Start date of ESA therapy +1)/7);

X will be defined as the duration of the effect of ESA following the last ESA administration for each ESA therapy use period, based on the following rules:

If Frequency = 1 PER WEEK then X=7

If Frequency = 2 PER WEEK then X=3

If Frequency = 3 PER WEEK then X=2

If Frequency = 1 PER MONTH then X=28

- If Frequency = ONCE then X=0
- If Frequency = BIM (Bi-monthly) then X=14
- If Frequency = QD (daily) then X=1
- If Frequency = QM (monthly) then X=28
- If Frequency = QOD (every other day) then X=2
- If Frequency = TID (three times daily) then X=1
- If Frequency = 4 TIMES PER WEEK then X=2
- If Frequency = EVERY 3 WEEKS then X=21

Additional frequency may be considered depending on the data.

6.1.3.8 Occurrence of iron supplementation.

The use of IV iron is collected in the Concomitant Medication form of the eCRF. All medications are coded with WHO-DD. Records selected will be those coded as IRON PREPARATIONS, and where route is INTRAVENOUS.

Having received IV Iron is a binary variable (Yes/No), where “Yes” is defined as having at least one record selected during the Efficacy Emergent Period. Time to first IV Iron will be derived similarly to time to first use of rescue therapy, in Section [6.1.3.7](#) with first event date corresponding to the Date of first dose of IV Iron during the efficacy emergent period. Censoring rules will be the same as for use of rescue therapy.

The Efficacy Emergent Period will be divided in periods of 28 days and for each of these periods, the monthly mean of IV iron will be calculated. The total amount of IV iron used will be calculated for the overall Efficacy Emergent Period. Only use of IV Iron that was ongoing or started during the Efficacy Emergent Period will be taken into account.

The Mean Monthly IV iron use per subject (in mg) for weeks 37 to 52 and 53-104 will be calculated similarly as in Section [6.1.2.3](#). The occurrence of oral iron (coded as IRON PREPARATIONS and route ORAL) use will be also derived by the relevant periods (week 1-36, week 37-52, week 53-104) as a yes or no use of oral iron. This will be combined with IV iron use for these periods.

6.1.3.9 Change from BL to each post-dosing study visit in Total cholesterol, LDL/High-density Lipoprotein (HDL) ratio, Non-HDL cholesterol, Triglycerides, Apolipoproteins A1 and B, ApoB/ApoA1 ratio.

For each sample, the following will be calculated:

- LDL/HDL ratio (LDL Cholesterol divided by HDL Cholesterol)
- Non-HDL cholesterol (Total Cholesterol minus HDL Cholesterol)

Change from baseline to each post-dosing study visit will be calculated for the following lipid parameters:

- Total cholesterol
- LDL cholesterol
- HDL cholesterol
- Low-density lipoprotein (LDL) / high-density lipoprotein (HDL) ratio
- Non-HDL cholesterol
- Triglycerides
- Apolipoproteins A1 and B (ApoA1 and ApoB)
- ApoB/ApoA1 ratio.

All available data will be summarized descriptively for all parameters above, for fasted values and regardless of fasting status.

No imputation will be performed in case of a missing value. If several values are available in the same window, one value will be used, as defined in [Table 34](#) and Section [7.11.4](#)

Baseline assessment is the assessment from Day 1 visit. If this value is missing, then the latest screening period value will be used as baseline.

6.1.3.10 Occurrence of mean LDL cholesterol <100 mg/dL calculated over weeks 12 to 28.

The evaluation period is defined as the average of all available LDL cholesterol values in weeks 12-28 (visit at 12, 20 and 28 weeks, as defined in [Table 34](#) and Section [7.11.4](#)). The occurrence of mean LDL cholesterol <100mg/dL (2.59 mmol/L) over weeks 12 to 28 will then be defined as a binary variable (Yes/No), where "Yes" is defined as mean LDL cholesterol <100mg/dL (2.59 mmol/L) over weeks 12 to 28.

No imputation will be performed in case of a missing value.

This endpoint will be reported on fasting values and regardless of fasting status.

6.1.3.11 Occurrence of achieved antihypertensive treatment goal in CKD subjects (SBP< 140 mmHg and DBP< 90 mmHg) based on the mean SBP and mean DBP calculated over weeks 12 to 28.

Occurrence of achieved antihypertensive treatment goal (SBP< 140 mmHg and DBP< 90 mmHg) based on the mean SBP and mean DBP will be calculated over an evaluation period defined as the average of all available values in weeks 12 to 28, similarly as in Section [6.1.2.6](#). The analysis windows is defined in [Table 32](#), Section [7.11.4](#)

Occurrence of achieved antihypertensive treatment goal will then be defined as a binary variable (Yes/No), where "Yes" is defined as SBP< 140 mmHg and DBP< 90 mmHg.

No imputation will be performed in case of a missing value.

6.1.3.12 Change from BL to the average value of weeks 12 to 28 in Quality of Life scores.

All study subjects will be required to complete Quality of Life (QoL) questionnaires as indicated in the schedule of assessments:

- SF-36
- FACT-An
- EQ-5D 5L

In HD subjects, questionnaires will be completed by the subject preferably prior to, or at the start of dialysis session. In Peritoneal Dialysis subjects, it is done preferably prior to any study assessment.

In addition to week 12-28, change from BL to the average value of weeks 36 to 52 will be calculated.

The next sections provide further details on how to derive these instruments, some derivations will be provided by an external vendor (QualityMetric).

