6.1.3 Additional Secondary Efficacy Endpoints

The additional secondary efficacy endpoints are listed in [Table 6](#)

Table 6 Additional Secondary Efficacy Endpoints

Number	Endpoint
	Hb Maintenance
1	Hb response during weeks 28 and 36 defined as mean Hb – regardless of use of rescue therapy within the target range of 10.0 to 12.0 g/dL. Additional definitions to be included for sensitivity analyses are mean Hb \geq 10.0 g/dL during Week 28 and 36, during Week 28 and 52 and mean Hb between 10.0 and 12.0 g/dL during Week 28-52.
2	Hb change from BL to each post-dosing time point.
3	Hb level averaged over weeks 28 to 36, 44 to 52, and 96 to 104 without use of rescue therapy within 6 weeks prior to and during these 8-week evaluation periods.
4	Hb change from BL to the average Hb value of weeks 28 to 36, 44 to 52, and 96 to 104 regardless of the use of rescue therapy.
5	Proportion of Hb values \geq 10 g/dL and within 10.0 to 12.0 g/dL in weeks 28 to 36, 44 to 52, and 96 to 104 without use of rescue therapy within 6 weeks prior to and during these 8-week evaluation periods.
	Hospitalizations
6	Occurrence (number) of hospitalizations (HD days are not counted as hospitalizations, even when performed overnight), number of days of hospitalization per patient-year exposure and time to first hospitalization.
	Rescue Therapy Use
7	Occurrence and time to first use of rescue therapy [composite of RBC transfusions (all patients) and rescue ESA (roxadustat treated subjects only)], occurrence and time to first use of RBC transfusions, number of RBC packs per subject, volume of RBC transfused per subject.
	Iron Use
8	Occurrence of IV iron supplementation. Mean monthly IV iron (mg) per subject during weeks 37-52 and weeks 53-104 (monthly defined as a period of 4 weeks). Use of oral iron.
	Change in Cholesterol Levels, Apolipoproteins
9	Change from BL to each post-dosing study visit in Total cholesterol, LDL/High-density Lipoprotein (HDL) ratio, Non-HDL cholesterol, Apolipoproteins A1 and B, ApoB/ApoA1 ratio.
10	Occurrence of mean LDL cholesterol $<$ 100 mg/dL calculated over weeks 12 to 28.
	Blood Pressure Effect
11	Occurrence of achieved antihypertensive treatment goal in CKD subjects (SBP $<$ 140 mmHg and DBP $<$ 90 mmHg) based on the mean SBP and mean DBP calculated over weeks 12 to 28.
	HRQoL

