7.11.6 End of Efficacy Emergent Period

For all subjects, the end of Efficacy Emergent Period is defined as the treatment period up to the EOT Visit. Only exception for subjects who discontinued due to death, the last Hb assessment is taken as per convention the date of death is the EOT visit.

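### Hospital days per year (SAP 6.1.3.6) counts whole stays but divides only by time in the Efficacy Emergent Period, so a subject can exceed 365 days per year; the denominator is also described inconsistently

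*SAP*

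**What the plan says.** SAP 6.1.3.6 introduces the variable with "The number of days of hospitalization per year treated will be calculated as" and gives a ratio for each subject. The numerator begins "Sum of the durations of all non-HD hospitalizations in days (Date of discharge", less the date of admission, plus one day. The denominator is the "duration of efficacy emergent period in days" divided by 365.25.

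SAP 7.11.6 fixes the end of that period: "the end of Efficacy Emergent Period is defined as the treatment period up to the EOT Visit". It adds: "Only exception for subjects who discontinued due to death, the last Hb assessment is taken".

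SAP 6.1.3.6 ties hospitalizations to the period in one sentence, "The occurrence and the number of non-HD hospitalizations per subject during the Efficacy Emergent Period will be calculated". That sentence covers occurrence and number. The days formula refers to all stays, and no sentence cuts a stay at the period end.

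Where dates are missing, "the hospitalization duration will be imputed by the average duration per stay derived from the subjects with non-missing duration within the same treatment group".

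The denominator appears in two other forms. SAP Table 6, item 6, has "number of days of hospitalization per patient-year exposure and time to first hospitalization". SAP 6.1.3.6 also points to treatment exposure in SAP 6.5.4, which runs from first to last dose, not to the EOT visit.

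Protocol 5.3.3.2 records admission and discharge dates, and keeps collecting hospitalization details after treatment in subjects who stopped early. SAP 7.4.3.6 reports days per year descriptively, and SAP 7.1 lists mean, SD, median, minimum and maximum.

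**The concern.** The two parts of the ratio cover different time. A stay that starts on treatment contributes every day to discharge, while the time at risk stops at EOT or at the last Hb. The mismatch falls on subjects who stop treatment or die around an admission: they have a short denominator and a stay that runs past it.

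The arm mean gives each subject's ratio equal weight, so a few short follow-ups with long stays can move it. It then partly reflects how many subjects stopped in hospital, not only how much time subjects spent in hospital on treatment. SAP 7.5.1.4 itself allows that discontinuation may differ between arms, and the trial is open-label, so the distortion need not cancel.

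The SAP matches the two parts elsewhere. IV iron (SAP 6.1.2.3) is cut at the earlier of week 36 and the period end in both numerator and denominator. AE event rates (SAP 6.2.1.5) are pooled events over total patient-years.

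The missing-date rule adds a smaller problem. An imputed stay has no upper limit from death, period end or last contact.

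**Working it through.** The documents give no expected value for this variable, so there is no planned figure to reproduce. The formulas, the 375 subjects per arm and the 104-week maximum come from the documents. All stay lengths, stop times and stop rates below are assumptions.

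**1. Single subjects.** As written: (discharge − admission + 1) / (P/365.25), with P the period in days. In-period: the same, with the stay cut at day P.

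| P (days) | Stay (study days) | Days counted | As written | Days in period | In-period |
|---|---|---|---|---|---|
| 25 | 20–60 | 41 | 41/(25/365.25) = 599.0 | 6 | 87.7 |
| 28 | 20–60 | 41 | 534.8 | 9 | 117.4 |
| 60 | 50–89 | 40 | 243.5 | 11 | 67.0 |
| 364 | 360–380 | 21 | 21.1 | 5 | 5.0 |

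A value above 365.25 needs only more counted days than period days. With truncation the ceiling is 365.25.

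**2. Deaths.** Suppose the last Hb is on day 29 and the terminal stay is days 30–60. If all stays count, the result is 31/(29/365.25) = 390.4, with no stay day inside the period. If only admissions within the period count, the stay contributes nothing. The text does not settle which applies.

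**3. Arm mean, fixed example.** Take 375 subjects, most with 10 days in 364 (10.03 per year). Let 19 (5%) stop at day 28 with a 41-day stay, 9 days of it inside the period.

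- As written: (19 × 534.8 + 356 × 10.03)/375 = 36.6. The 19 subjects supply 74% of the mean.
- Truncated: (19 × 117.4 + 356 × 10.03)/375 = 15.5.
- Truncated and pooled: (19 × 9 + 356 × 10)/[(19 × 28 + 356 × 364)/365.25] = 10.5.

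If the same 19 instead stop at day 84 with a 21-day stay, the mean as written is 14.2 and their share is 33%.

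**4. Arm mean, simulation.** Inputs: one admission per year, geometric stays with mean 10 days, exponential stopping, period from 7 to 728 days. In-hospital stops add a stay with 1 to 4 days inside the period. There are 60,000 subjects per setting.

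| Stop hazard per year | Stops in hospital | Mean as written | Mean truncated | Inflation | Pooled, truncated |
|---|---|---|---|---|---|
| 0.10 | 0% | 9.98 | 9.76 | 2% | 9.82 |
| 0.25 | 0% | 10.06 | 9.68 | 4% | 9.84 |
| 0.40 | 0% | 9.98 | 9.52 | 5% | 9.82 |
| 0.10 | 30% | 11.65 | 10.11 | 15% | 9.88 |
| 0.25 | 30% | 13.93 | 10.50 | 33% | 10.01 |
| 0.40 | 30% | 16.12 | 10.89 | 48% | 10.07 |

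At hazard 0.25, subjects with under 12 weeks are about 5.5% of the arm. They supply 6% of the mean as written when stops are unrelated to stays, and 22% when 30% of stops are in hospital. A second illustration assumes 25% stopping before week 52, 40% of those during an admission, and mean stay 14 days. It gives 16.6 against 12.5, also +33%.

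**5. Between arms.** Let both arms share admission rate and stay length, with 30% of stops in hospital, and differ only in stop hazard (0.25 against 0.40). The difference as written is 16.12 − 13.93 = 2.19 days per year. Truncated means differ by 10.89 − 10.50 = 0.39, and pooled truncated rates by 10.07 − 10.01 = 0.06.

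**The case against.** The strongest reply is that little depends on this number. It is part of one additional secondary endpoint, outside the fixed sequence in SAP Table 17, and is reported without a test. The median, minimum and maximum accompany the mean, and SAP 7.4.3.6 also reports total duration, average stay and number of hospitalizations. The comparative analysis is time to first hospitalization, which uses the admission date. All of this stands and limits the impact.

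A reader might infer that early stoppers must dominate the arm means. The documents do not support that. They give no admission rate, stay length or frequency of stopping in hospital. In the examples above the early stoppers' share ranges from 6%, in line with their numbers, to 74%. It reaches 86% only if 10% of an arm stops at day 28, each with a 41-day stay. Nor do the documents show which arm would be favoured.

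It can also be argued that counting the full length of a stay begun on treatment is a legitimate choice, since truncation drops days from the very stays that accompanied stopping. That is reasonable, but it calls for a denominator covering the same days. Hospital data continue after EOT in premature discontinuers, so a longer matched period is possible. It does not justify a whole-stay numerator over a shorter denominator.

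Finally, nothing says that discharge dates will be blank when a subject dies in hospital. How often the missing-date rule would apply is unknown.

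**Conclusion.** The formula is wrong as written, not merely short of detail. It sets untruncated stays against a truncated period and can return more than 365 hospital days per year. It gives subjects who stop or die around an admission disproportionate weight in the unweighted mean.

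The size depends on inputs that the documents do not supply. At a stop hazard of 0.25 per year, inflation is about 4% with stopping unrelated to stays and about 33% with 30% of stops in hospital. Over hazards of 0.10 to 0.40 the corresponding ranges are 2% to 5% and 15% to 48%. Dominance by early stoppers is possible under harsh inputs but is not a consequence of the formula.

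The denominator inconsistency between Table 6, the formula and the reference to SAP 6.5.4 needs no assumptions and should be corrected in any case. The impact stops at a descriptive summary. No tested claim changes, and time to first hospitalization is unaffected.

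**What to change.** - Count days from the later of admission and first dose to the earliest of discharge, death and the end of the period used in the denominator.
- Where the discharge date is missing, cap the imputed stay at the earliest of death, period end and last contact.
- State one denominator in Table 6, in the SAP 6.1.3.6 formula and in its cross-reference to exposure. State also whether a stay is selected by its admission date, which settles the death cases.
- Report total in-period days over total patient-years by arm alongside the per-subject summary, because truncation alone still leaves an unweighted mean of ratios. A negative binomial model is optional for a descriptive variable.

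The cost is SAP wording and a small programming change, with no new data. The drawback is that hospital days after the period end leave this rate, including terminal stays after the last Hb if the Efficacy Emergent Period is kept. They can be listed separately.
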